10.4.5 Baseline Descriptive Statistics

All demographic and clinical characteristics of participants and tumor will be summarized and tabulated. Pre-BCI peripheral blood T cell levels and expression of surface and intracellular markers will be measured. Continuous data such as measured levels of T cell subsets will be presented with means and standard deviations. Categorical data such as presence of an activated effector-like phenotype will be presented with frequencies and percentages.

10.4.6 Planned Interim Analysis

10.4.6.1 Safety Review

Ongoing safety review will occur as part of the 3+3 dose escalation scheme, which requires evaluation of dose-limiting toxicities in order to escalate to the next dose or de-escalate to a lower dose.

10.4.6.2 Efficacy Review

Our primary focus will be on safety and feasibility. Formal interim analyses to review for efficacy will not be performed.

10.4.7 Additional Sub-Group Analyses

Sub-group analyses as described below will employ Wilcoxon signed-rank tests as described above for secondary analyses. In particular:

- 1) We will compare changes in pre- and post BCI peripheral blood CD8⁺ T cells expressing a combination of Ki67⁺,PD-1+, HLA-DR⁺, CD38⁺, and Bcl-2^{low} at each dose level.
- 2) In the subset of participants receiving active treatment (radiation therapy, chemotherapy, and/or immunotherapy in the past 30 days) for non-small cell lung cancer, we will investigate if the combination of cryoablation and his/her current treatment will lead to enhanced increases in the percent of CD8⁺ T cells expressing a combination of Ki67⁺,PD-1+, HLA-DR⁺, CD38⁺, and Bcl-2^{low} compared to participants treated with BCI alone.

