2.2.3 BCI Dose Rationale

BCI of peripheral lung tumors has not been performed previously. To maximize safety, the initial freeze time is shorter than standard freeze times for cryobiopsy of peripheral lesions (15). Our dose escalation will initiate patients at a safe freeze time for which there is extensive clinical experience with related procedures. If there is no complication from this, in the next cohort of patients we will gradually escalate dose to those higher than are routinely performed in bronchoscopic cryobiopsy.

CONFIDENTIAL

Freeze times will be escalated up to 30 seconds based on tolerability. In comparison, freeze times of up to 20 minutes have been safely administered during percutaneous cryoablation of peripheral lung tumors (7, 10). Although an optimal freeze time duration is unknown, longer freeze times may be needed in order to induce anti-tumor immune responses. Based on tolerability, freeze times will be increased as described in the following table:

| Dose Level | Freeze Time (per site) | Thaw Time |
|------------|------------------------|---|
| Level 1 | 1 second | Will last until the probe separates from target |
| | | tissue* |
| Level 2 | 2 seconds | Will last until the probe separates from target |
| | | tissue* |
| Level 3 | 3 seconds | Will last until the probe separates from target |
| | | tissue* |
| Level 4 | 5 seconds | Will last until the probe separates from target |
| | | tissue* |
| Level 5 | 10 seconds | Will last until the probe separates from target |
| | | tissue* |
| Level 6 | 20 seconds | Will last until the probe separates from target |
| | | tissue* |
| Level 7 | 30 seconds | Will last until the probe separates from target |
| | | tissue* |

* Thaw times at each dose level will be captured for each site.

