4.2.3 Sub-Set Analysis and Exploratory Endpoints

- Investigation of changes in peripheral blood CD8⁺ T cells displaying a combination of Ki67⁺, PD-1+, HLA-DR⁺, CD38⁺, and Bcl-2^{low} after BCI at each dose level. This sub-set analysis will investigate if there is an optimal freeze time duration for inducing anti-tumor immune responses.
- 2) Investigation of changes in peripheral blood CD8⁺ T cells displaying a combination of Ki67⁺,PD-1+, HLA-DR⁺, CD38⁺, and Bcl-2^{low} after BCI at each dose level. This sub-set analysis will investigate if the combination of cryoablation and current active cancer treatment will lead to enhanced increases in percent of peripheral blood CD8⁺ T cell expression of PD-1 and Ki67 and/or CD8⁺ T cells displaying an activated effector-like phenotype.

5 Study Enrollment and Withdrawal

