6.1.2 Dose Escalation Protocol

A standard 3+3 dose escalation strategy will be used. The table below shows the doses that will be provided. Three participants will be initially enrolled at Level 1. If none of the first three participants at a given dose experiences dose-limiting toxicity (DLT), the dose will be escalated. If two or more of the first three participants experience DLT, the prior dose will be deemed the maximum tolerated dose (MTD) and the study will be terminated. If one of the first three participants experiences DLT, an additional three participants will be enrolled at the same dose. If among these six, only one experiences DLT, the dose will be terminated. If two or more of six experience DLT, the prior dose will be deemed the MTD and the study will be terminated. If the MTD is reached and only three participants have been treated at that dose, an additional three will be treated to ensure six subjects are treated at the MTD. DLT are defined in Section 4.1.1 (Primary Study Endpoints: Feasibility and Safety).

| Dose Level | Freeze Time (per site) | Thaw Time |
|------------|------------------------|---|
| Level 1 | 1 second | Will last until the probe separates from target tissue* |
| Level 2 | 2 seconds | Will last until the probe separates from target tissue* |
| Level 3 | 3 seconds | Will last until the probe separates from target tissue* |
| Level 4 | 5 seconds | Will last until the probe separates from target tissue* |
| Level 5 | 10 seconds | Will last until the probe separates from target tissue* |
| Level 6 | 20 seconds | Will last until the probe separates from target tissue* |

CONFIDENTIAL

| Level 7 | 30 seconds | Will last until the probe separates from target |
|---------|------------|---|
| | | tissue* |

6.1.3 **Procedures for Training of Clinicians on Procedural Intervention**

The NYU Interventional Pulmonary service has extensive experience using the flexible cryoprobe for debulking of central airway tumors. BCI will be performed by a board-certified, NYU Interventional Pulmonologist.

Only patients with the presence of a bronchus or airway path leading directly to the peripheral lung tumor will be eligible to undergo BCI. The peripheral tumor will also need to be identified by radial EBUS prior to performing BCI. If the peripheral tumor is unable to be identified by radial ultrasound within 20 minutes, then the patient will not be a candidate to undergo BCI.

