10.2 Statistical Hypotheses

- 1) BCI will be feasible and safe, with a maximum tolerated dose to be determined in this trial.
- 2) Post-BCI peripheral blood will demonstrate an increase in the percent of CD8⁺ T cells expressing a combination of Ki67⁺, PD-1+, HLA-DR⁺, CD38⁺, and Bcl-2^{low} compared to pre-BCI peripheral blood CD8⁺ T cells.
- 3) CD8+ T cell responses to BCI will be greater among subjects with high PD-1 expressing T cells in BAL effluent.

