10.4 Description of Statistical Methods

10.4.1 General Approach

- Continuous data will be summarized with means and standard deviations.
- Categorical data will be summarized with frequencies and percentages.
- *P* values will be considered statistically significant at the 0.05 level. Note that the study is designed to determine the MTD, and thus is not powered to detect statistically significant differences in any of the secondary outcomes.

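### The per-level signed-rank tests in 10.4.7(1) cannot answer the optimal-freeze-time question: a level of three cannot reach 0.05, and no planned test compares levels

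*Combined protocol and SAP*

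**What the plan says.** Section 4.2.3 gives the purpose of the dose-level immune analysis: "This sub-set analysis will investigate if there is an optimal freeze time duration for inducing anti-tumor immune responses". Section 2.2.3 explains the interest in freeze time: "longer freeze times may be needed in order to induce anti-tumor immune responses".

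Section 10.4.7 names the method: "Sub-group analyses as described below will employ Wilcoxon signed-rank tests as described above for secondary analyses". Its first item begins "We will compare changes in pre- and post BCI peripheral blood" and applies the comparison to the activated CD8+ subset at each dose level. No between-level or trend test is named there or elsewhere in section 10. Section 10.4.1 says that P "values will be considered statistically significant at the 0.05 level", without giving sidedness. The related hypothesis in 10.2 is directional: "Post-BCI peripheral blood will demonstrate an increase in the percent of CD8".

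Cohort sizes come from 6.1.2: "If none of the first three participants at a given dose experiences dose-limiting toxicity (DLT), the dose will be escalated". After one DLT in the first three, "an additional three participants will be enrolled at the same dose". The MTD level is topped up to six.

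Section 10.4.4 applies the same test to paired pre- and post-BCI blood over all participants. Section 6.1.1 states that there is no control group.

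**The concern.** There are two separate problems. First, the signed-rank test on three pairs has so few possible outcomes that none falls below 0.05. That differs from low power, because no effect size could produce a significant result. Second, the question is comparative and the test is not. A set of within-level results says which levels showed a detectable change, and detectability depends on cohort size.

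Cohort size in a 3+3 design is set by toxicity. The only levels able to show p<0.05 are those expanded after a DLT and the MTD level. A reader who scans a table of per-level p values could take that pattern for a freeze-time effect. Section 10.5 expects the results to inform later combination studies, so the pattern could carry forward.

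A related wording issue affects the pooled test. Without a control group, a pre/post shift describes the whole procedure, not freezing alone.

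**Working it through.** **The plan's own figure.** Section 10.5 gives about 80% power for 15 subjects, a 0.75 SD difference and a within-subject correlation of 0.5.
- SD of the paired difference = √(2(1−0.5)) = 1.0 SD, so the standardised effect is 0.75.
- Two-sided normal approximation: Φ(0.75·√15 − 1.96) = Φ(0.945) = 0.83.
- Two-sided paired t: 0.77, reaching 0.80 at n=16 or at 0.78 SD.
- Exact signed-rank on normal data, simulated: about 0.75.

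The figure is reasonable as an approximation. It concerns the pooled comparison, not the dose levels.

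**Smallest attainable p within a level.** With n untied, non-zero differences, the most extreme result is all n in one direction. Its exact p value is 2/2ⁿ two-sided and 1/2ⁿ one-sided.

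| Pairs | Two-sided | One-sided |
|---|---|---|
| 3 | 0.25 | 0.125 |
| 4 | 0.125 | 0.0625 |
| 5 | 0.0625 | 0.031 |
| 6 | 0.031 | 0.016 |

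A large-sample approximation does not rescue n=3. The rank-sum variance is 3·4·7/24 = 3.5, so z = 3/√3.5 = 1.60, giving p = 0.109 two-sided and 0.054 one-sided.

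At n=6 the next two-sided value is 0.0625, so all six must move the same way. Simulated two-sided power at n=6 is about 0.21 for a 0.75 SD change and 0.87 for 2 SD.

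**How many levels stay at three.** Seven levels of three plus three more at the MTD is 7×3+3 = 24, the target in 10.5. A level expands after exactly one DLT in three with probability 3p(1−p)². This is 0.14, 0.24 and 0.38 at true DLT rates of 5%, 10% and 20%, so most low-toxicity levels stay at three.

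Pairs can also be lost. Section 7.1.2 collects no post-BCI blood from treated patients found not to have NSCLC, and 5.7.2 discards samples when a participant withdraws after the post-BCI draws. A level of six that loses one pair has a two-sided minimum of 0.0625.

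**What an ordered-dose test would offer.** Assumptions: change scores with SD 1, three participants at levels 1-6 and six at level 7, two-sided 0.05, and a Spearman or Kendall test of change against level (simulation).

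| True pattern across levels | Power |
|---|---|
| Linear rise of 0.75 SD | about 22% |
| Linear rise of 1.0 SD | about 34-36% |
| Linear rise of 1.5 SD | about 66-68% |
| Linear rise of 2.0 SD | about 89% |
| Peak of 1.5 or 2 SD at level 4, zero at levels 1 and 7 | about 5-6% |
| Zero at level 1, 1.5 SD from level 2 on | about 17-18% |

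With 15 participants over five levels (5.6 gives 15-24), a 1.5 SD rise has about 44% power and 2 SD about 66%.

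**Pooled test.** If the rest of the procedure shifted the marker with no BCI effect at all, the pooled signed-rank test would reject as follows. The shift sizes are assumptions.

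| Assumed non-BCI shift | n=15 | n=24 |
|---|---|---|
| 0.25 SD | 14% | 21% |
| 0.5 SD | 42% | 63% |
| 0.75 SD | 75% | 93% |

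**The case against.** The strongest reply is that the plan promises little here. Section 4.2.3 is headed sub-set and exploratory, 10.4.1 says the study is not powered for secondary outcomes, and 10.5 says the sample cannot settle the immune endpoint. Sections 10.1 and 10.4.8 add graphics and individual listings. This limits the consequence, and it stands. It does not make a test that cannot reject at n=3, and does not compare levels, suitable for a question about levels.

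A second reply is that a trend test is no full answer. An optimum may be non-monotone, and a monotone test then does no better than chance. Dose level also follows calendar order and ignores the number of freeze-thaw cycles and the two probe sizes (6.1.1). All of this stands, so the limits belong in the text.

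A third reply concerns attribution. A reader might infer that the freeze-time gradient is the only internal evidence linking a change to BCI. It is not. Section 4.2.2 plans a virus-specific T-cell control (influenza and EBV tetramers, CEF stimulation) aimed at non-specific activation, and 6.1.1 records ice-ball formation for each patient. The control does not exclude antigen release by biopsy, but it is relevant. Nor does everyone have biopsies: section 2.2 plans diagnostic biopsies where NSCLC is not already proven. Bronchoscopy (5.1), BAL (7.1.1) and general anesthesia (2.2) are common to all.

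**Conclusion.** The point holds for 10.4.7(1). At a level left at three, significance at 0.05 is unattainable at any effect size, one- or two-sided. At six it is attainable only with complete agreement in direction (two-sided, no ties or lost pairs). No planned analysis compares freeze times. These results are exact and need no assumption about effect size. The power figures for a trend test and for the pooled test do rest on the assumed unit-SD changes and cohort layout.

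Three stronger readings are not supported. It is not true that no level can reach 0.05, since 6.1.2 yields six at the MTD and after one DLT in three. The plan has no rule that declares the immune objective met or chooses a freeze time from p values; the MTD is set by DLTs alone (6.1.2, 10.4.3). And a BCI-related response should not have to depend on a positive trend, because a real effect similar across most freeze times would usually give a negative trend test. Lack of a control group is an openly stated phase I choice. The issue there is only how the pooled result is described.

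**What to change.** In 10.4.7(1):
- Remove the per-level p values and show each participant's change from day 0 by dose level, descriptively.
- Add one exploratory analysis of change against ordered dose level over all participants with paired samples, by Jonckheere-Terpstra or Spearman. State the sidedness and whether day 7 or day 14 is used.
- State its limits: it targets a monotone relation and would miss a mid-range optimum, power is low for modest gradients, and dose level is confounded with calendar order.

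In 10.4.4, describe the pooled result as change after bronchoscopy with BCI, noting the shared bronchoscopy, BAL and anesthesia and the biopsies in some participants. Interpret it alongside the virus-specific control in 4.2.2. Do not require a positive trend before a BCI-related response may be reported.

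The cost is wording only: no added participants, samples or assays. The trade-off is that the plan gives up nominal per-level p values for one test that may well be inconclusive, particularly if enrollment ends near 15.

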and the low electronic noise of the system. (The technology provides better resolution than alternate cytometry technologies, like mass cytometry (CyTOF), with higher throughput, less cell loss, and a more robust hardware platform.) [name] developed a number of antibody staining panels for the system, including a panel that assesses many immune checkpoint molecules at once, and a pan-cytokine/global T-cell activation panel. Table 1 lists the markers studied with each panel. There are three notable advantages of highly multiplexed flow cytometry panels like these. First, they allow broad screening of many markers in order to find the most sensitive biomarkers in a particular disease setting. Second, by finely and precisely characterizing combined expression of every marker studied at the single cell level, a more detailed, mechanistic understanding of responses is possible than with serum, secretion, or bulk population assays. Finally, the technology is sample sparing; it provides maximal information (about protein expression) from a single vial of cells; this will be important given the relatively low numbers of cells collected from BAL. Though a number of institutions now have high-parameter flow cytometry technology, these panels have not been successfully developed elsewhere, and those institutions do not have [name] expertise in application of this technology.

Although this approach is novel in immuno-oncology, there is precedent, particularly from studies of vaccine responses. In healthy individuals, baseline peripheral blood CD8⁺ T cell HLA-DR⁺CD38⁺ and Ki67⁺Bcl-2^{low} expression is 0.5-2% and less than 0.5%, respectively (26). After immunization of healthy volunteers with the smallpox vaccine, up to 40% of peripheral blood CD8⁺ T

cells displayed HLA-DR⁺CD38⁺Ki67⁺Bcl-2^{low} (26). Similarly, in 29 patients with advanced NSCLC started on PD-1/PDL-1 axis inhibitory antibodies, approximately 70% of patients had a 1.5-fold increase in peripheral blood Ki67⁺CD8⁺ T cells demonstrating high levels of expression of DR⁺CD38⁺ Bcl-2^{low} and PD-1 post-treatment (27). Approximately 25-80% of these responding Ki67⁺CD8⁺PD-1⁺T cells expressed intra-cellular granzyme B, consistent with cytotoxic potential (27). Epstein-Barr Virus (EBV) -specific CD8⁺T cells had minimal activation and proliferation after PD-1 targeted therapy suggesting these CD8⁺

CONFIDENTIAL

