5.1 Inclusion Criteria

In order to be eligible to participate in this study, an individual must meet all of the following criteria:

- Biopsy-proven, advanced, inoperable non-small cell lung cancer (stages IIIA/B/C and IVA/B based on the 8th edition TNM staging guidelines) or suspected inoperable non-small cell lung cancer (stage as defined above) who may undergo on-site pathology review of tissue specimen obtained at time of diagnostic and staging bronchoscopy.
 - If on-site pathology review is not feasible or is unable to confirm the diagnosis of nonsmall cell lung cancer, patients with high-risk features for the diagnosis of non-small cancer including past or current cigarette smoking, history of COPD, spiculated lesion with bronchus sign on chest CT, presence of mediastinal/hilar adenopathy or evidence of distant metastatic disease on chest CT scan or PET CT scan may be included.
- Pre-procedure chest CT scan with the presence of an airway path leading directly to the peripheral lung tumor (also known as a "bronchus sign"), and the peripheral lung tumor will need to be visualized by radial endobronchial ultrasound at time of bronchoscopy
- Undergoing bronchoscopy for diagnostic and/or palliative purpose unrelated to this study
- Age of 22 years or older
- Ability to provide informed consent
- Concomitant chemotherapy, immunotherapy, and/or radiation therapy are allowed
- ECOG performance status of ≤2

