7.1.2 Standard of Care Study Procedures

Pre-BCI screening:

- Medical history (including cancer and cancer treatment history, co-morbidities, functional status, and social history)
- Medication and treatment history (specifically if patient is on a platelet inhibitor other than aspirin
 or anticoagulant), and if patient has previously or is currently receiving chemotherapy, radiation
 therapy, or immunotherapy.
- Physical examination (vital and full physical exam will be performed by clinical team prior to determining patient's fitness for undergoing bronchoscopy
- Chest CT assessment to evaluate for the presence of a bronchus or airway path leading directly to the peripheral lung tumor
- Screening laboratory evaluation as described in Section 7.2
- Pre-BCI blood collection for immune analysis

During bronchoscopy:

• Bronchoalveolar lavage (BAL) will be performed in two locations, which are the regions of the primary tumor and of the distal portion of the same lung. BAL is a standard of care component of routine bronchoscopy for lung cancer.

CONFIDENTIAL

- If there is no pre-existing biopsy-proven non-small cell lung cancer diagnosis, on-site pathology review of a tissue biopsy obtained during bronchoscopy may be performed, if technically feasible or if the patient does not have high risk features for possible non-small cell lung cancer (see above).
- After the standard-of-care portion of the bronchoscopy is complete, the peripheral tumor will need to be identified by radial EBUS. If the peripheral tumor cannot be identified within 20 minutes, then BCI will not be performed.
- BCI will be performed in eligible candidates

Post-BCI:

- Monitor for any adverse events from day 0 to day 7 Post-BCI blood collection for immune analysis on day 7 ± 3
- Post-BCI blood collection for immune analysis on day 14 ± 3
- Patients who undergo BCI and are found not to have non-small cell lung cancer will be monitored for adverse events from day 0 to day 7 and be followed up at a standard of care pose-bronchoscopy visit within 7 ± 3 days. These patients will not have post-BCI blood collected.

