7.4 Concomitant Medications, Treatments, and Procedures

All concomitant prescription medications taken during study participation will be recorded on the case report forms (CRFs). For this protocol, a prescription medication is defined as a medication that can be prescribed only by a properly authorized/licensed clinician. Medications to be reported in the CRF are concomitant prescription medications, over-the-counter medications and non-prescription medications.

In treatment naïve patients undergoing a diagnostic bronchoscopy, enrollment in this study will not lead to a delay in appropriate, standard of care treatment. Involvement in this study is not anticipated to preclude enrollment in any other ongoing clinical trial. In patients undergoing a diagnostic or therapeutic bronchoscopy who are already receiving treatment with chemotherapy, radiation, or immunotherapy, combination therapy with BCI could theoretically affect anti-tumor immune responses.

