10.3 Analysis Datasets

All participants who were treated with BCI will be included.

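### The pre/post immune test keeps samples drawn after new anticancer therapy has started, and the 30-day treatment window has no anchor date, so a therapy effect can be read as a BCI effect

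*Combined protocol and SAP*

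**What the plan says.** **Who is analysed, and how.** Section 10.3 reads: "All participants who were treated with BCI will be included". Section 10.4.4 applies a Wilcoxon signed-rank test to the paired blood measurements, with no covariate and no rule about treatment begun after BCI. Section 6.1.1 confirms that there is no control group.

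**When blood is drawn.** Before BCI on day 0, then at day 7 and day 14, each ±3 days (4.2.2). Post-BCI samples can therefore fall anywhere from day 4 to day 10 and from day 11 to day 17.

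**What treatment is permitted.** Section 5.1: "Concomitant chemotherapy, immunotherapy, and/or radiation therapy are allowed". For treatment-naïve patients at diagnostic bronchoscopy, 7.4 states that "enrollment in this study will not lead to a delay in appropriate, standard of care treatment". Section 7.6 restricts only antiplatelet and anticoagulant drugs.

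**What the plan knows about the marker.** Section 2.1 (part VI) describes 29 patients with advanced NSCLC starting PD-1/PD-L1 antibodies, of whom "approximately 70% of patients had a 1.5-fold increase in peripheral blood" Ki67+CD8+ T cells with high HLA-DR/CD38, low Bcl-2 and PD-1. That is the phenotype named in hypothesis 2 of 10.2.

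**How treatment status enters the analysis.** Only through the second subgroup in 10.4.7. It takes participants with "radiation therapy, chemotherapy, and/or immunotherapy in the past 30 days" and asks whether their marker rise is larger "compared to participants treated with BCI alone". Section 7.1.2 asks at pre-BCI screening "if patient has previously or is currently receiving chemotherapy, radiation therapy, or immunotherapy". Section 7.4 notes that "combination therapy with BCI could theoretically affect anti-tumor immune responses", but only for patients already on treatment at bronchoscopy.

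**The concern.** A single-arm pre/post comparison attributes to the intervention whatever changes between the two samples. Here one foreseeable change is the start of systemic therapy or radiation, and for one class of drug the protocol's own background says it moves the measured endpoint upwards. The plan recognises that treatment matters, but only when it was already under way at BCI.

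Two analyses are exposed. In the pooled test of 10.4.4, a rise caused by new therapy counts as a BCI response. In the comparison of 10.4.7, new starters classed with the BCI-alone group would raise that group's response and mask any difference from the treated subset.

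The stake is interpretive. Section 10.5 says the results will inform later trials of BCI with anti-PD-1 therapy. An anti-PD-1 effect credited to BCI would mislead that particular decision.

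**Working it through.** **1. The plan's own figure.** Section 10.5 gives 15 subjects, about 80% power, 0.75 SD and correlation 0.5.
- SD of the paired difference = SD × √(2(1 − 0.5)) = SD, so the standardised effect is 0.75.
- Normal approximation, two-sided 0.05 (sidedness is not stated): n = ((1.960 + 0.842)/0.75)² ≈ 13.95, so 14. Power at n=15 is Φ(0.75√15 − 1.960) = Φ(0.945) = 82.8%.
- Paired t: 77.1% at n=15 and 80.1% at n=16.

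The planning figure is reasonable. It assumes that the whole paired difference is due to BCI.

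**2. Is there any rule for new therapy?** Sections 5.1, 7.4, 7.6, 10.3, 10.4.4 and 10.4.7, read together, contain no exclusion, censoring, reclassification or sensitivity analysis for therapy begun between day 0 and a post-BCI draw.

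**3. What does the 30-day window mean?**
- *Anchored at BCI.* This fits the reference to current treatment in 10.4.7 and the screening question in 7.1.2. New starters then fall outside the active subset and so into the BCI-alone group.
- *Anchored at each draw.* New starters move into the active subset.

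The text does not choose between them. The first is the more natural reading. The pooled test in 10.4.4 is affected under either.

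**4. Illustrative size in the pooled test.** From the documents: 70% of PD-1/PD-L1 starters with a 1.5-fold rise, two-sided 0.05, total enrolment 15–24 (5.6). Assumed: n=20 pairs, the share starting therapy before the draw, and an SD of the log fold-change of 0.3 or 0.5. With no BCI effect, each log fold-change is Normal(0, SD), plus log(1.5) = 0.405 for a starter who responds. The test is the exact two-sided signed-rank. With no starters it rejects in about 5% of simulated trials.

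| Share of starters showing the full rise by the draw | Log SD | 20% start | 30% start | 50% start |
|---|---|---|---|---|
| 70% (upper end) | 0.3 | 9% | 15% | 35% |
| 70% (upper end) | 0.5 | 7% | 9% | 18% |
| 35% (assumed half) | 0.3 | 6% | 7% | 12% |
| 35% (assumed half) | 0.5 | 5% | 6% | 8% |

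In the upper-end rows nearly all rejections are in the direction of an apparent BCI benefit. With 30% starting and 70% responding, the spurious mean log shift is 0.30 × 0.70 × 0.405 = 0.085, an apparent rise of about 9%.

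**5. Cross-check at the plan's n=15.** Here k participants start therapy and each shifts by 0.75, 1.0 or 1.5 SD of the paired difference (assumed).
- k=3: 6.8%, 8.2%, 10.4%.
- k=5: 11.3%, 15.7%, 24.3%.
- k=8: 24.1%, 36.5%, 60.9%.

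For scale, a 1.5-fold rise is 0.405/0.5 = 0.81 SD or 0.405/0.3 = 1.35 SD. In this check every starter shifts, so it is harsher than the table.

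**The case against.** **The window may already be adequate.** Someone who began therapy on day 5 has not, in ordinary words, had BCI alone, and a window anchored at the draw would capture that person. This stands. A reader might infer that 10.4.7 has a rule counting new starters as BCI alone, but it contains no such rule, only an unanchored window whose natural reading has that result.

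**The upper-end rates assume too much.** They treat every starter as taking a checkpoint inhibitor and showing the full response by the draw. Section 2.1 links the cited responses to the first 4 weeks of therapy, whereas a new starter here has at most about 10 days of therapy by the first draw and 17 by the second. The protocol describes these drugs as first-line only for selected patients. Others may start chemotherapy or radiation, for which no effect on this marker is given. Some participants have only suspected NSCLC at bronchoscopy, so nothing in the documents supports half of them starting within two weeks. All of this stands, and it is why the lower rows matter.

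**The endpoint is secondary.** Sections 10.4.1 and 10.5 say that the study is not powered for it, and 10.4.8 lists individual data. True, and it limits the consequence. Low power does not guard against bias, however, and 10.4.1 still declares significance at 0.05.

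**The restricted analysis is not a clean BCI effect.** A participant who began a checkpoint inhibitor shortly before BCI may still have a rising marker, and that person stays in. This also stands.

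**Conclusion.** The concern holds in a limited form. As written, the plan leaves samples drawn after new anticancer therapy in an unadjusted, uncontrolled pre/post test of a marker that, by the protocol's own account, PD-1/PD-L1 antibodies raise. It also leaves the treatment window in 10.4.7 without an anchor.

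The size cannot be stated from the documents. Over the assumptions tried at n=20, the false-positive rate runs from about 5% (no material inflation) to about 35%. The result depends on the share starting therapy, the type of therapy, how much of the response appears by the draw, and the marker SD.

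A reader might take the 35% as the expected error rate. The documents do not support that, because it needs half the participants to start a checkpoint inhibitor and respond at the full cited rate within the draw window. A reader might also infer that start dates are already on file. Sections 7.3.4 and 7.4 provide for cancer treatment history and concomitant medications, but neither mentions start dates, and radiation is not a medication.

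Feasibility, DLT and MTD analyses are unaffected. The change is worth making because it is cheap and the results are meant to guide BCI plus anti-PD-1 trials.

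**What to change.** - **Section 10.4.4:** prespecify a paired analysis restricted to post-BCI samples drawn before any new systemic anticancer therapy or radiation. Report it beside the all-sample analysis, separately for day 7 and day 14, with the number of samples removed.
- **Section 10.4.7:** state the anchor date. Classify participants by therapy in the 30 days before BCI or started before the post-BCI sample, and show new starters separately from BCI alone.
- **CRF:** confirm that the type and start date of anticancer therapy, including radiation, are recorded up to each draw. Add the fields if they are not.
- **Reporting:** name therapy begun shortly before BCI as a residual confounder that the restricted analysis does not remove.

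The cost is a few sentences of analysis plan, one further analysis run and possibly a small CRF addition. Some samples drop out of the restricted analysis, which lowers its precision. The analysis could also select patients who start therapy later, so both analyses should be shown. No visit, procedure or treatment changes.
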